7.2 Pre-treatment

Within 28 days of study treatment initiation (Cycle 1 Day 1):

- Sign informed consent including optional biopsy consent.
- Medical history
- Physical exam
- Weight
- Vital signs
- ECOG performance status ([APPENDIX I](#))
- Hematology
- Blood chemistry
- Urinalysis
- Electrocardiogram (ECG) (for this and all other timepoints, a standard 12-lead ECG is taken while patient is in a semi-recumbent position)
- Confirmation of KRAS mutation:
 - Optional for Part A dose levels 1-4 (0.15 mg/kg, 0.3 mg/kg, 0.6 mg/kg, and 1.2 mg/kg). Depending upon availability and patient consent, we may request archival tumor sample and/or results of genomic tumor profile, but these are not required to confirm patient eligibility for Part A.
 - Requirement for Part A dose level 5 (1.6 mg/kg) and all patients in Part B. Genomic tumor profile results can be used. Otherwise, a tumor tissue sample (archival or fresh) can be tested locally for eligibility. Fresh biopsy (if needed) may be obtained only if it has minimal risk of complications for the patient. If such type of biopsy is needed but cannot feasibly be collected, the Sponsor and Medical Monitor should be consulted.
 - Liquid biopsy may also be used to confirm KRAS status. In the case that both a liquid and tumor biopsy is available, the following criteria will be used to evaluate eligibility:

		Tumor	
		Wildtype	Mutant
Liquid	Wildtype	Fails Inclusion # 1	Meets Inclusion # 1
	Mutant	Meets Inclusion # 1	Meets Inclusion # 1

- Collect samples to be used for exploratory biomarkers to measure GST family members including GSTP.
- GSTT1 samples will also be collected for both Parts A and B, but GSTT1 genotype will only be used for stratification in Part B.
- Optional tumor biopsy.
- Concomitant medications

Within 14 days of study treatment initiation (Cycle 1 Day 1):

- Imaging for tumor measurements

Within 7 days of study treatment initiation (Cycle 1 Day 1):

- Pregnancy test

7.3 During Treatment

Each patient must remain in clinic to be monitored for infusion related reactions after receiving a dose of NBF-006. A 6-hour safety observation period is required after completion of the first dose in both Part A and Part B. The observation period after subsequent doses may be reduced, as detailed in Section 8.1.2.8.

After completion of at least 3 cycles of study treatment (i.e., after receiving ≥ 12 doses of NBF-006 over the course of 18 weeks), no more than one dose of NBF-006 may be omitted during a cycle for convenience reasons (to improve patient's quality of life), at the investigator's discretion after discussion with medical monitor.

7.3.1 Cycle 1

7.3.1.1 Week 1 (Day 1, first dose)

- Physical Exam (may be done within 3 days prior)
- Weight (may be done within 3 days prior)
- Vital signs
- ECG
- ECOG (may be done within 3 days prior)
- Hematology (may be done within 3 days prior)
- Blood chemistry (may be done within 3 days prior)
- Urinalysis (may be done within 3 days prior)
- Immune activation biomarkers (pre- and post-dose; see Section 8.6)
- Anti-drug antibody (ADA) assay sampling (pre-dose)
- PK blood sampling (pre- and post-dose; see Section 8.3)
- Blood sample for GSTP KD (pre- and post-dose, see Section 8.8)
- NBF-006 administration
- Concomitant medications
- AEs

7.3.1.2 Week 2 (Day 8 \pm 3)

- Vital signs
- Hematology
- Blood chemistry

- PK blood sampling (pre-dose)
- Blood sample for GSTP KD (pre-dose)
- NBF-006 administration
- Concomitant medications
- AEs

7.3.1.3 Week 3 (Day 15 ± 3)

- Vital signs
- Hematology
- Blood chemistry
- ADA assay sampling (pre-dose)
- NBF-006 administration
- Concomitant medications
- AEs

7.3.1.4 Week 4 (Day 22 ± 3)

- Vital signs
- ECG
- Hematology
- Blood chemistry
- PK blood sampling (pre- and post-dose)
- NBF-006 administration
- Concomitant medications
- AEs
- Optional biopsy 24 (±3) hours after completion of the 4th dose in cycle 1.

7.3.1.5 Weeks 5 (Day 29-35)

Rest

7.3.1.6 Week 6 (Day 36-42)

- Tumor measurement (use same method as baseline) performed at the end of every even cycle for Part A dose levels 1-4 and performed at the end of every cycle for Part A dose level 5 and all patients in Part B.

7.3.2 Cycle 2

7.3.2.1 Week 1 (Day 1 should occur within 3 days of Day 42 of previous cycle)

- Physical Exam
- Weight

- Vital signs
- ECOG
- Hematology
- Blood chemistry
- Urinalysis
- Pregnancy test
- ADA assay sampling (pre-dose)
- PK blood sampling (pre-dose)
- NBF-006 administration
- Concomitant medications
- AEs

7.3.2.2 Week 2 (Day 8 ± 3)

- Vital signs
- Hematology
- Blood chemistry
- NBF-006 administration
- Concomitant medications
- AEs

7.3.2.3 Week 3 (Day 15 ± 3)

- Vital signs
- Hematology
- Blood chemistry
- NBF-006 administration
- Concomitant medications
- AEs

7.3.2.4 Week 4 (Day 22 ± 3)

- Vital signs
- Hematology
- Blood chemistry
- NBF-006 administration
- Concomitant medications
- AEs

7.3.2.5 Week 5 (Day 29-35)

Rest

7.3.2.6 Week 6 (Day 36-42)

- Tumor measurement (use same method as baseline) performed at the end of every even cycle for Part A dose levels 1-4 and performed at the end of every cycle for Part A dose level 5 and all patients in Part B.

7.3.3 Cycle 3 and Beyond

7.3.3.1 Week 1 (Day 1 should occur within 3 days of Day 42 of previous cycle)

- Physical Exam
- Weight
- Vital signs
- ECOG
- Hematology
- Blood chemistry
- Urinalysis
- Pregnancy test
- ADA assay sampling pre-dose every even numbered cycle, e.g., Cycle 4, Cycle 6, Cycle 8, etc.) up to 1 year. Year 2 collection occurs every 6 months.
- NBF-006 administration
- Concomitant medications
- AEs

7.3.3.2 Week 2 (Day 8 ± 3)

- NBF-006 administration
- Concomitant medications
- AEs
- Perform safety exams (e.g., vital signs, hematology, blood chemistries) as clinically indicated

7.3.3.3 Week 3 (Day 15 ± 3)

- NBF-006 administration
- Concomitant medications
- AEs
- Perform safety exams (e.g., vital signs, hematology, blood chemistries) as clinically indicated

7.3.3.4 Week 4 (Day 22 ± 3)

- NBF-006 administration
- Concomitant medications

- AEs
- Perform safety exams (e.g., vital signs, hematology, blood chemistries) as clinically indicated

7.3.3.5 Week 5 (Day 29-35)

Rest

7.3.3.6 Week 6 (Day 36-42)

- Tumor measurement (use same method as baseline) performed at the end of every even cycle for Part A dose levels 1-4 and performed at the end of every cycle for Part A dose level 5 and all patients in Part B.

7.4 End of Treatment (to be performed within 30 ± 3 days after last treatment)

The following assessments will be performed for all patients who are terminating treatment due to any reason. The End of Treatment (EOT) visit should be performed immediately after the patient discontinues treatment and should be no later than 30 ± 3 days after the last dose.

- Physical Exam
- Weight
- Vital signs
- ECG
- ECOG
- Tumor measurement (use same method as baseline)
- Hematology
- Blood chemistry
- Urinalysis
- Pregnancy test
- ADA assay sampling
- Concomitant medications
- AEs

7.5 30 Day Safety Follow up Visit (±3)

- Physical Exam
- Weight
- ECOG
- Hematology
- Blood chemistry
- Urinalysis

- ADA assay sampling
- AEs

If the EOT visit is performed 30 ± 3 days after the last dosing, the safety follow-up visit can be omitted.

8.0 STUDY ASSESSMENTS

8.1 Safety Assessments

8.1.1 Safety Analysis

Safety data will be tabulated for all patients and include vital signs, laboratory parameters, and AEs.

8.1.2 Reporting of Adverse Events

8.1.2.1 Adverse Events

An AE is any untoward medical occurrence in a patient or clinical investigation subject administered a pharmaceutical product that does not necessarily have a causal relationship with the treatment. An AE can be any unfavorable and unintended sign (including a laboratory finding), symptom or disease temporally associated with the use of a medicinal (investigational) product, whether or not related to the medicinal (investigational) product.

The AE reporting period starts on Cycle 1 Day 1; if an AE occurs before the first dose of study drug it will be considered a non-treatment emergent AE. At each evaluation, patients should be interviewed in a non-directed manner to elicit potential adverse reactions from the patient. The occurrence of an AE will be based on changes in the patient's physical examination, laboratory results, and/or signs and symptoms.

All AEs (except Grade 1 and 2 laboratory abnormalities that do not require an intervention), regardless of causal relationship, are to be recorded in the eCRF and source documentation. The Investigator must determine the intensity of any AEs according to the NCI CTCAE Version 5.0 ([APPENDIX II](#)) and their causal relationship. Those AEs not covered by these criteria will be graded as follows:

1. Mild: Discomfort noticed, but no disruption of normal daily activity. Prescription drug not ordinarily needed for relief of symptom but may be given because of personality of patient.
2. Moderate: Discomfort sufficient to reduce or affect normal daily activity. Patient is able to continue in study; treatment for symptom may be needed.

3. Severe: Incapacitating, severe discomfort with inability to work or to perform normal daily activity. Severity may cause cessation of treatment with test drug; treatment for symptom may be given and/or patient hospitalized.
4. Life-Threatening: Symptom(s) place the patient at immediate risk of death from the reaction as it occurred; it does not include a reaction that, had it occurred in a more serious form, might have caused death.
5. Fatal: Event caused the death of the patient.

AEs will be followed until resolution or stabilization while the patient remains on-study. Once the patient is removed from study, events thought to be related to the study medication will be followed until resolution or stabilization, unless, in the Investigator's opinion the event is unlikely to resolve due to the patient's underlying disease, or until the patient starts a new treatment regimen or the patient is lost to follow-up.

8.1.2.2 Attribution Definitions

An AE is considered to be associated with the use of the Investigational Product if the attribution is determined as possible, probable or definite. Attribution of AEs will be recorded in the eCRF as:

- Unrelated: The AE is clearly NOT related to the study treatment.
- Unlikely: The AE is doubtfully related to the study treatment.
- Possible: The AE may be related to the study treatment.
- Probable: The AE is likely related to the study treatment.
- Definite: The AE is clearly related to the study treatment.

8.1.2.3 Definition of an Unexpected Adverse Event

An unexpected AE is defined as any adverse drug experience, the specificity or severity of which is not consistent with the current IB; or, if an IB is not required or available, the specificity or severity of which is not consistent with the risk information described in this protocol or in the regulatory agency study authorization application.

Unexpected, as used in this definition, refers to an adverse drug experience that has not been previously observed (e.g., included in the IB) rather than from the perspective of such experience not being anticipated from the pharmacological properties of the pharmaceutical product.

8.1.2.4 Serious Adverse Event

An SAE is defined as any untoward medical occurrence that at any dose:

1. Results in death,
2. Is life-threatening (i.e., the patient was at risk of death at the time of the event. It does not refer to an event which hypothetically might have caused death if it was more severe),
3. Requires in-patient hospitalization or prolongation of existing hospitalization excluding that for pain management, disease staging/re-staging procedures, or catheter placement unless associated with other serious events,
4. Results in persistent or significant disability/incapacity, or
5. Is a congenital anomaly/birth defect.

Important medical events that may not result in death, be life-threatening, or require hospitalization may be considered serious adverse drug events when, based on appropriate medical judgment, they may jeopardize the patient or subject and may require medical or surgical intervention to prevent one of the outcomes listed above.

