2.6 Potential Risks and Benefits

As this is the first-in-man study of NBF-006, no human data regarding the safety or potential benefit of NBF-006 was available before the study started. Since the clinical study began, 14 patients (IB v 4.0, 26MAR2021) have been treated at dose levels 1-4 (0.15 mg/kg, 0.3 mg/kg, 0.6 mg/kg, and 1.2 mg/kg) without any signs of overt toxicity. No clinically meaningful immune activation (complement and cytokines) was observed at dose levels 1-4 (0.15 mg/kg, 0.3 mg/kg, 0.6 mg/kg, and 1.2 mg/kg).

Nucleic acids like the siRNA are rapidly degraded by nucleases when not protected by LNPs. Much of the potential toxicity of NBF-006 would result from the LNP components

themselves. Many clinical studies of LNP-formulated siRNAs have observed dose-dependent inflammatory cytokine elevations.¹² Although many early phase trials of similar LNP-formulated siRNAs demonstrated a tolerable safety profile, immunogenicity (e.g., immune responses) could be a potential toxicity of this study treatment, especially at high doses or with frequent dosing of NBF-006.¹³

Based on other clinical trials with LNP-encapsulated siRNAs, the following are possible risks of NBF-006:

- Elevated cytokine levels or complement activation which could lead to inflammation. The symptoms would be flu-like symptoms, such as back pain, fever, nausea, headache, rash, rapid heartbeat, low blood pressure, temporary tightness in the chest, and trouble breathing. In severe cases, cytokine release syndrome could potentially develop.
- Allergic reaction (rash, wheezing, shortness of breath, heart palpitations, swelling of the face, and lowered blood pressure) to the drug or one of the drug or LNP components.
- In animals, NBF-006 administration led to increased vacuolation in tissues and cells. The appearance of vacuoles was not associated with any changes in organ function and went away over time.

Please see the current IB for further details about the potential risks and benefits associated with this study.

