8.1.2.7 Reporting of Serious Adverse Events

AEs classified as serious require expeditious handling and reporting to Theradex Oncology to comply with regulatory requirements.

For any SAE that occurs while a patient is on-study; within 30 days of the last study drug administration, regardless of any opinion as to the relationship of the SAE to the study drug; or if any SAE that the Investigator feels is related to the study drug occurs later than 30 days after the last study drug administration, the Theradex Oncology Safety Desk must be notified immediately (within 24 hours of becoming aware of the event) by email, fax or telephone. Notification by email is preferred. The email address, fax and telephone numbers listed below may be used during both business and non-business hours. During non-business hours a recorded message will provide the telephone caller with the contact information for the on-call monitor.

All SAEs require that a Serious Adverse Event Report Form be completed and forwarded either via facsimile or as a PDF via email to Theradex Oncology at the fax number or email listed below within 24 hours of becoming aware of the event.

SAEs will be reported to: Theradex Oncology Safety Desk
[contact]
[contact]
Email: [contact]

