8.1.2.8 Post-Infusion Observation Period

Observe/monitor for any signs and symptoms of IRRs, such as back pain, fever and/or shaking chills, flushing and/or itching, alterations in heart rate and blood pressure, dyspnea or chest discomfort, skin rashes, or anaphylaxis (e.g., generalized urticaria, angioedema, wheezing, hypotension, tachycardia, etc.).

During Part A of the study, each patient must remain in clinic for a minimum 6-hour safety observation period after each NBF-006 infusion until at least three patients at a specific dose level have been reviewed by the Safety Review Committee.

Reductions in the observation period at a given dose level may be recommended by the Safety Review Committee (consisting of Investigators, Theradex Oncology Medical Monitor, and Sponsor) after at least three patients have received a full cycle of treatment (defined as at least four doses and 2-week drug holiday) at that dose level.

Recommendations by the Safety Review Committee for a reduced observation period will be contingent upon:

- Absence of any significant safety concerns following a complete review of all clinical and laboratory data for all treated subjects at the given dose level and the preceding dose levels,
- Absence of any late-onset (>2 hours post-dose) IRRs or IRR symptoms that continue beyond 2 hours post-dose, and lack of any severe or serious IRRs,
- Review and consideration of cytokine and complement activation data at the given dose prior to making a recommendation to shorten the observation period.

If the Safety Review Committee recommends a reduced observation period, the minimum observation period allowed will be 2 hours following EOI from Cycle 2 onward during Part A of the study. Further reductions in the observation period may be suggested by the safety review committee as additional data has accumulated.

For Part B of the study, each patient must remain in clinic for a 6-hour safety observation period after the first dose, 2 hours after EOI for remaining doses in Cycle 1. The observation period may be further reduced to 30 minutes starting Cycle 2, after Medical Monitor and Investigator safety review. The observation period may be lengthened, if clinically indicated.

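### The SAE definition excludes hospitalisation for pain management without limiting it by cause or timing, so an admission solely for possibly drug-related pain can be classed as non-serious

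*Protocol*

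**What the plan says.** Section 8.1.2.4 lists five seriousness criteria. The third is in-patient or prolonged hospitalisation, "excluding that for pain management, disease staging/re-staging procedures, or catheter placement unless associated with other serious events". A further paragraph covers important medical events, which "may be considered serious adverse drug events when, based on appropriate medical judgment" they could jeopardise the patient and need intervention to prevent a listed outcome.

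Two other sections name pain as a possible sign of a drug effect:
- Section 8.1.2.8 tells sites to watch for infusion-reaction signs "such as back pain, fever and/or shaking chills, flushing and/or itching".
- Section 2.6 describes cytokine or complement activation, a possible risk drawn from other trials of lipid-nanoparticle siRNAs, as flu-like symptoms "such as back pain, fever, nausea, headache, rash, rapid heartbeat, low blood pressure, temporary tightness in the chest".

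Section 8.1.2.7 requires SAEs to reach the safety desk within 24 hours. While the patient is on study and for 30 days after the last dose, this applies whatever the presumed relationship to study drug. Under section 8.1.2.1, AEs other than minor laboratory abnormalities, "regardless of causal relationship, are to be recorded in the eCRF and source documentation".

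**The concern.** Exclusions of this kind usually serve to keep routine cancer-care admissions out of expedited reporting, and the neighbouring items (staging, catheter placement) fit that purpose. The pain item as worded goes further. It depends only on the reason for admission and not on whether the pain is old or new, planned for or unexpected, or due to tumour or drug.

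For this product the protocol itself presents pain as a possible early sign of infusion reaction or immune activation. A patient admitted only for control of new back pain after an infusion could be filtered out by the reason for admission, before the reporting rule of section 8.1.2.7, which disregards causality, can apply. At stake are the serious label, its tabulation and the speed with which the safety desk hears of the event, in a first-in-human trial with small cohorts.

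**Working it through.** No arithmetic applies. The protocol states no SAE rate and no calculation that depends on one. The check takes a test case through the text.

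**Test case.** New back pain after an infusion, possibly related, admitted only for pain control, with no other serious event.

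**Step 1: the seriousness criteria (8.1.2.4).**
- Death, life-threatening, disability, congenital anomaly (criteria 1, 2, 4, 5): not met.
- Hospitalisation (criterion 3): removed by the pain-management exclusion.
- The exception within criterion 3 requires association with another serious event. There is none, so it does not bring the case back.
- Important medical event: available, but permissive and dependent on judgement. It is framed around events that may fall short of hospitalisation, so it does not oblige an investigator to reverse what criterion 3 has just excluded.

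The case is therefore non-serious unless the investigator chooses otherwise.

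**Step 2: what depends on that label.**

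| Use | Section | Depends on seriousness? |
|---|---|---|
| SAE counts | 8.1.2.4 | Yes |
| 24-hour report | 8.1.2.7 | Yes |
| Shorter Part A observation: no serious infusion reactions | 8.1.2.8 | Yes, for this limb |
| Same decision: no severe reactions, none starting or persisting beyond 2 hours, no significant safety concern | 8.1.2.8 | No |
| AE recording and grading | 8.1.2.1 | No |
| Attribution | 8.1.2.2 | No |
| Medical Monitor review | 8.1.2.10 | No; covers non-serious AEs too |
| DLT assessment, Part A | 6.1.3 | No; generally by grade and relatedness |
| Clearing 1.6 mg/kg | 6.1.1 | No; 0-1 DLT in 6 patients |
| Safety stopping rule | 8.1.2.11 | No; Grade 5 toxicity |
| Primary safety endpoints | 9.2.1 | No; DLTs and AEs, SAE counts not named |

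**Step 3: can other channels replace the lost report?** Only in part. DLT assessment is confined to the first 42 days and the section is headed Part A, so it does not cover later cycles. Medical Monitor review follows reporting by the site, and section 12.2 asks only that eCRF data be submitted in a timely manner. Neither carries the 24-hour duty.

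**Step 4: how many admissions?** Not derivable. The only experience given (section 2.4) is 14 patients at dose levels 1-4, with no treatment-related SAE, no treatment-related Grade 3-4 AE and one Grade 2 infusion reaction after which treatment could continue. This says nothing about how often patients are admitted for pain.

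**The case against.** The strongest reply is that the affected set is very small. An admission to treat or observe an infusion reaction is naturally an admission for the reaction, not for pain management. The clause sits among routine oncology admissions and would probably be read that way. The same sentence restores admissions tied to other serious events, and investigators may still use medical judgement. Infusion reactions also have their own observation periods and grade-based management. The observation-shortening decision has limbs for severe, late-onset and persistent reactions that do not need the serious label, and a pain reaction leading to admission would often trigger one of them.

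Most of this stands. It narrows the point to admissions for pain control alone, where the link to the drug may not be recognised at the time. It does not remove the point: the likely intent is not written into the sentence, and the remaining route to seriousness is optional.

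A reader might infer more than the text supports:
- **That every pain admission is lost.** The exception and the judgement clause rule that out.
- **That the primary safety endpoints or the clearance of 1.6 mg/kg are biased.** They rest on AEs and DLTs, which do not use seriousness.
- **That possibly related events escape causality assessment or Medical Monitor review.** Sections 8.1.2.2 and 8.1.2.10 apply to non-serious AEs as well.
- **That the SAE rate is understated by a known amount.** One case is 1/10 = 10 percentage points in a cohort of ten and 1/6 = 16.7 points in a cohort of six. That is the weight of any single event, not an expected bias.
- **That the absence of treatment-related SAEs in section 2.4 reflects the exclusion.** The same section reports no treatment-related Grade 3-4 AE, a statement that does not depend on the SAE definition.

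**Conclusion.** The wording is too broad and should be corrected, but the consequence is limited. An admission solely for new, possibly drug-related pain can be classed as non-serious. It would then miss the SAE tabulation, the 24-hour report and the serious-reaction limb of the observation condition, unless the investigator elects the important-medical-event route. AE recording, attribution, Medical Monitor review, the AE and DLT endpoints and the grade-based DLT decisions are unaffected.

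The size cannot be estimated from the protocol. The conclusion assumes that sites apply the exclusion as written, by reason for admission. If all sites read it as covering only cancer-related or planned pain care, nothing would be lost, but the text does not secure that reading. This is a low-cost improvement to safety reporting and does not call the trial's analyses into question.

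**What to change.** In section 8.1.2.4, limit the pain-management exclusion to admissions planned before the first dose, or for pain control of the underlying cancer or another pre-existing condition. Add that an unplanned admission for new or worsened pain not clearly due to the underlying disease is an SAE. This brings the definition into line with the symptom lists in sections 2.6 and 8.1.2.8. Repeat the rule in the guidance for the SAE report form.

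The change takes one or two sentences and alters no treatment, visit or assessment. The cost is a few more SAE reports, some for pain that later proves to be due to the tumour.
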